#### **6.2.2. Laboratory Safety Tests**

Safety laboratory tests will be performed as described in the protocol.

To determine if there are any clinically significant laboratory abnormalities, the haematological, clinical chemistry (serum) and urinalysis safety tests will be assessed against

the criteria specified in the sponsor reporting standards. The assessment will take into account whether each participant's baseline test result is within or outside the laboratory reference range for the particular laboratory parameter.

Baseline will be defined as the measurement on Day -1 of each period of Part 1 and Part 3, and treatment phase of Part 2, or the last available corresponding pre-dose collection time point including unplanned measurements (whichever occurs later).

### **6.2.3. Vital Signs**

Single supine blood pressure, pulse rate, oral temperature and respiratory rate measurements will be taken at times detailed in the Schedule of Activities given in the protocol.

Baseline will be defined as pre-dose measurement on Day 1 of each period of Part 1 and Part 3, and treatment phase of Part 2 or the last available corresponding pre-dose collection time point including unplanned measurements (whichever occurs later).

The following vital signs endpoints will be determined:

- Actual value of supine (and orthostatic if measured) systolic and diastolic blood pressure, pulse rate, oral temperature and respiratory rate at each time point.
- Change from baseline in supine (and orthostatic if measured) systolic and diastolic blood pressure, pulse rate, oral temperature and respiratory rate at each time point.
- The maximum decrease and increase from baseline over all measurements taken post-dose for supine systolic and diastolic blood pressures, pulse rate, oral temperature and respiratory rate.

The maximum increase from baseline will be calculated by first subtracting the baseline value from each post-dose measurement to give the change from baseline. The maximum of these values over the respective period will then be selected, except in the case where a subject does not show an increase. In such an instance, the minimum decrease should be taken.

Similarly, the maximum decrease from baseline will be determined by selecting the minimum value of the changes from baseline. In cases where a subject does not show a decrease, the minimum increase should be taken.

### **6.2.4. ECG and Telemetry**

#### ECG

A single 12-lead ECG will be obtained on all subjects at screening.

TriPLICATE 12-lead ECGs will be recorded on all subjects at all other time points as detailed in the Schedule of Activities given in the protocol.

The QT, heart rate, QTcF, PR, RR and QRS will be recorded at each assessment time.

If not supplied, QTcF will be derived using Fridericia's heart rate correction formula:

$$\text{QTcF} = \text{QT} / (\text{RR})^{1/3} \quad \text{where RR} = 60/\text{HR} \text{ (if not provided)}$$

The average of the triplicate readings collected at each assessment time will be calculated for each ECG parameter. Baseline will be defined as the average of the triplicate pre-dose recordings collected on Day 1 of each period of Part 1 and Part 3, and treatment phase of Part 2.

The maximum absolute value (post-dose) and the maximum increase from baseline for QT, heart rate, QTcF, PR and QRS, will be determined over all measurements taken post-dose for QTcF, PR and QRS.

The maximum increase from baseline will be calculated by first subtracting the baseline value from each post-dose measurement to give the change from baseline. The maximum of these values over the respective period will then be selected, except in the case where a subject does not show an increase. In such an instance, the minimum decrease should be taken.

Changes from baseline for the ECG parameters QT interval, heart rate, QTcF interval, PR interval, and QRS interval will also be calculated.

### Telemetry

*To establish a baseline, telemetry should be recorded for at least 2 hours before dosing in Period 1 of Part 1, and subsequently collected for 12 hours after the dosing.*

All abnormal rhythms will be recorded and reviewed by the study physician for the presence of rhythm of potential clinical concerns, which will document the time, duration and description of the clinically significant event.

### **6.2.5. Other Safety Data**

Additional safety data will be collected as described in the protocol and will be listed if collected in the sponsor's database.

### **6.3. Pharmacokinetic Endpoints**

Blood samples for PK analysis of PF-07059013 will be taken according to the Schedule of Activities given in the protocol. The following PK parameters will be calculated for PF-

07059013 (if possible) for Part 1 and Part 3 (Table 1), and Part 2 (Table 2, Table 3) from the concentration-time values using standard non-compartmental methods.

**Table 1. Plasma and Blood PK Parameters for Part 1 and Part 3 (Single Dose)**

Parameter	Definition	Method of Determination
CC 1		
CC 2		
CC 3		
CC 4		
CC 5		
CC 6		
CC 7		
CC 8		
CC 9		
CC 10		
CC 11		
CC 12		
CC 13		
CC 14		
CC 15		
CC 16		
CC 17		
CC 18		
CC 19		
CC 20		
CC 21		
CC 22		
CC 23		
CC 24		
CC 25		
CC 26		
CC 27		
CC 28		
CC 29		
CC 30		
CC 31		
CC 32		
CC 33		
CC 34		
CC 35		
CC 36		
CC 37		
CC 38		
CC 39		
CC 40		
CC 41		
CC 42		
CC 43		
CC 44		
CC 45		
CC 46		
CC 47		
CC 48		
CC 49		
CC 50		
CC 51		
CC 52		
CC 53		
CC 54		
CC 55		
CC 56		
CC 57		
CC 58		
CC 59		
CC 60		
CC 61		
CC 62		
CC 63		
CC 64		
CC 65		
CC 66		
CC 67		
CC 68		
CC 69		
CC 70		
CC 71		
CC 72		
CC 73		
CC 74		
CC 75		
CC 76		
CC 77		
CC 78		
CC 79		
CC 80		
CC 81		
CC 82		
CC 83		
CC 84		
CC 85		
CC 86		
CC 87		
CC 88		
CC 89		
CC 90		
CC 91		
CC 92		
CC 93		
CC 94		
CC 95		
CC 96		
CC 97		
CC 98		
CC 99		
CC 100		
CC 101		
CC 102		
CC 103		
CC 104		
CC 105		
CC 106		
CC 107		
CC 108		
CC 109		
CC 110		
CC 111		
CC 112		
CC 113		
CC 114		
CC 115		
CC 116		
CC 117		
CC 118		
CC 119		
CC 120		
CC 121		
CC 122		
CC 123		
CC 124		
CC 125		
CC 126		
CC 127		
CC 128		
CC 129		
CC 130		
CC 131		
CC 132		
CC 133		
CC 134		
CC 135		
CC 136		
CC 137		
CC 138		
CC 139		
CC 140		
CC 141		
CC 142		
CC 143		
CC 144		
CC 145		
CC 146		
CC 147		
CC 148		
CC 149		
CC 150		
CC 151		
CC 152		
CC 153		
CC 154		
CC 155		
CC 156		
CC 157		
CC 158		
CC 159		
CC 160		
CC 161		
CC 162		
CC 163		
CC 164		
CC 165		
CC 166		
CC 167		
CC 168		
CC 169		
CC 170		
CC 171		
CC 172		
CC 173		
CC 174		
CC 175		
CC 176		
CC 177		
CC 178		
CC 179		
CC 180		
CC 181		
CC 182		
CC 183		
CC 184		
CC 185		
CC 186		
CC 187		
CC 188		
CC 189		
CC 190		
CC 191		
CC 192		
CC 193		
CC 194		
CC 195		
CC 196		
CC 197		
CC 198		
CC 199		
CC 200		
CC 201		
CC 202		
CC 203		
CC 204		
CC 205		
CC 206		
CC 207		
CC 208		
CC 209		
CC 210		
CC 211		
CC 212		
CC 213		
CC 214		
CC 215		
CC 216		
CC 217		
CC 218		
CC 219		
CC 220		
CC 221		
CC 222		
CC 223		
CC 224		
CC 225		
CC 226		
CC 227		
CC 228		
CC 229		
CC 230		
CC 231		
CC 232		
CC 233		
CC 234		
CC 235		
CC 236		
CC 237		
CC 238		
CC 239		
CC 240		
CC 241		
CC 242		
CC 243		
CC 244		
CC 245		
CC 246		
CC 247		
CC 248		
CC 249		
CC 250		
CC 251		
CC 252		
CC 253		
CC 254		
CC 255		
CC 256		
CC 257		
CC 258		
CC 259		
CC 260		
CC 261		
CC 262		
CC 263		
CC 264		
CC 265		
CC 266		
CC 267		
CC 268		
CC 269		
CC 270		
CC 271		
CC 272		
CC 273		
CC 274		
CC 275		
CC 276		
CC 277		
CC 278		
CC 279		
CC 280		
CC 281		
CC 282		
CC 283		
CC 284		
CC 285		
CC 286		
CC 287		
CC 288		
CC 289		
CC 290		
CC 291		
CC 292		
CC 293		
CC 294		
CC 295		
CC 296		
CC 297		
CC 298		
CC 299		
CC 300		
CC 301		
CC 302		
CC 303		
CC 304		
CC 305		
CC 306		
CC 307		
CC 308		
CC 309		
CC 310		
CC 311		
CC 312		
CC 313		
CC 314		
CC 315		
CC 316		
CC 317		
CC 318		
CC 319		
CC 320		
CC 321		
CC 322		
CC 323		
CC 324		
CC 325		
CC 326		
CC 327		
CC 328		
CC 329		
CC 330		
CC 331		
CC 332		
CC 333		
CC 334		
CC 335		
CC 336		
CC 337		
CC 338		
CC 339		
CC 340		
CC 341		
CC 342		
CC 343		
CC 344		
CC 345		
CC 346		
CC 347		
CC 348		
CC 349		
CC 350		
CC 351		
CC 352		
CC 353		
CC 354		
CC 355		
CC 356		
CC 357		
CC 358		
CC 359		
CC 360		
CC 361		
CC 362		
CC 363		
CC 364		
CC 365		
CC 366		
CC 367		
CC 368		
CC 369		
CC 370		
CC 371		
CC 372		
CC 373		
CC 374		
CC 375		
CC 376		
CC 377		
CC 378		
CC 379		
CC 380		
CC 381		
CC 382		
CC 383		
CC 384		
CC 385		
CC 386		
CC 387		
CC 388		
CC 389		
CC 390		
CC 391		
CC 392		
CC 393		
CC 394		
CC 395		
CC 396		
CC 397		
CC 398		
CC 399		
CC 400		
CC 401		
CC 402		
CC 403		
CC 404		
CC 405		
CC 406		
CC 407		
CC 408		
CC 409		
CC 410		
CC 411		
CC 412		
CC 413		
CC 414		
CC 415		
CC 416		
CC 417		
CC 418		
CC 419		
CC 420		
CC 421		
CC 422		
CC 423		
CC 424		
CC 425		
CC 426		
CC 427		
CC 428		
CC 429		
CC 430		
CC 431		
CC 432		
CC 433		
CC 434		
CC 435		
CC 436		
CC 437		
CC 438		
CC 439		
CC 440		
CC 441		
CC 442		
CC 443		
CC 444		
CC 445		
CC 446		
CC 447		
CC 448		
CC 449		
CC 450		
CC 451		
CC 452		
CC 453		
CC 454		
CC 455		
CC 456		
CC 457		
CC 458		
CC 459		
CC 460		
CC 461		
CC 462		
CC 463		
CC 464		
CC 465		
CC 466		
CC 467		
CC 468		
CC 469		
CC 470		

**Table 2. Plasma and Blood PK Parameters for Part 2 (Multiple Doses)**

CCI [REDACTED]

[REDACTED]	[REDACTED]	[REDACTED]	[REDACTED]
[REDACTED]	[REDACTED]	[REDACTED]	[REDACTED]
[REDACTED]	[REDACTED]	[REDACTED]	[REDACTED]
[REDACTED]	[REDACTED]	[REDACTED]	[REDACTED]
[REDACTED]	[REDACTED]	[REDACTED]	[REDACTED]

#### 6.4. PD Endpoints

Change from baseline and percent change from baseline will be calculated for all biomarkers. Baseline will be defined as the pre-dose value collected on Day 1. Blood samples will be collected for measurement of p20 and p50 as specified in the SoA.

CCI [REDACTED]

[REDACTED]
[REDACTED]
CCI [REDACTED]
[REDACTED]
[REDACTED]

##### 6.6.1. Immunogenicity

Immunogenicity will not be assessed in this study.

CCI [REDACTED]

[REDACTED]
[REDACTED]

## 7. HANDLING OF MISSING VALUES

For the analysis of safety endpoints, the sponsor data standard rules for imputation will be applied.

### **7.1. Concentrations Below the Limit of Quantification**

In all data presentations (except listings), concentrations below the limit of quantification (BLQ) will be set to zero. (In listings BLQ values will be reported as “<LLQ”, where LLQ will be replaced with the value for the lower limit of quantification). For PK calculations, BLQ will be handled by the Pfizer standard processes.

### **7.2. Deviations, Missing Concentrations and Anomalous Values**

In summary tables and plots of median profiles, statistics will be calculated having set concentrations to missing if one of the following cases is true:

1. A concentration has been collected as ND (ie not done) or NS (ie no sample),
2. A deviation in sampling time is of sufficient concern or a concentration has been flagged anomalous by the pharmacokineticist.

Note that summary statistics will not be presented at a particular time point if more than 50% of the data are missing.

### **7.3. Pharmacokinetic Parameters**

Actual PK sampling times will be used in the derivation of PK parameters.

If a PK parameter cannot be derived from a subject's concentration data, the parameter will be coded as NC (ie not calculated). (Note that NC values will not be generated beyond the day that a subject discontinues.)

In summary tables, statistics will be calculated by setting NC values to missing; and statistics will be presented for a particular dose with  $\geq 3$  evaluable measurements.

If an individual subject has a known biased estimate of a PK parameter (due for example to an unexpected event such as dosing error), this will be footnoted in summary tables and will not be included in the calculation of summary statistics or statistical analyses.

## **8. STATISTICAL METHODOLOGY AND STATISTICAL ANALYSES**

CCI

## 8.2. Statistical Analyses

### 8.2.1. Pharmacokinetic Analysis

To assess the pharmacokinetics of PF-07059013, the PK parameters detailed in Section 6.3 will be listed and summarized for subjects in the PK parameter analysis set (as defined in Section 5.2.2). Missing values will be handled as detailed in Section 7. Each PK parameter will be summarized for each Part by dose, treatment group (where applicable) and day (where applicable). Summary will include the set of summary statistics as specified in Table 4 for the single dose and Table 5 for the repeat-dosing, respectively.

**Table 4. PK Parameters to be Summarized Descriptively for Part 1 and Part 3 (Single Dose)**

Parameter*	Summary Statistics
CCI	
C max , CCI	
CCI	N, arithmetic mean, median, cv%, standard deviation, minimum, maximum, geometric mean and geometric cv%.
T max	N, median, minimum, maximum.
C	CCI
C	

\*Dose normalized parameters are only applicable to Part 1

**Table 5. PK Parameters to be Summarized Descriptively for Part 2 (Multiple Doses)**

Parameter	Summary Statistics
CCI C max , CCI	
CCI	N, arithmetic mean, median, cv%, standard deviation, minimum, maximum, geometric mean and geometric cv%.
T max	N, median, minimum, maximum.
C	
C	
I	

There will be 1 summary table for each part of the study presenting all PK parameters. The treatment subheading will include the cohort number and dose information.

For Part 1, dose normalized (to 1 mg) CCI Cmax will be plotted against dose (using a log scale) and will include individual subject values and the geometric means for each

dose. For Part 2, dose normalized (to 1 mg) **CCI**  $C_{max}$  will be plotted against dose (using a log scale) for each Day (1, 7 and 14), and will include individual subject values and the geometric means for each dose. Geometric means will have a different symbol than the individual values. A footnote will be added to the plots to indicate that geometric means are presented. The main analyses of Part 1, Part 2 and Part 3 data are descriptive in nature.

Presentations for blood and plasma PF-07059013 concentrations will include:

- A listing of all concentrations sorted by study Part, treatment, subject ID, and nominal time post-dose. The concentration listing will also include the actual collection times.
- Median concentrations time plots (on both linear and semi-log scales) against nominal time post-dose by dose and cohort (all doses on the same plot per scale, based on the summary of concentrations by dose and time post-dose).
- Mean concentrations time plots (on both linear and semi-log scales) against nominal time post-dose by dose (all doses on the same plot per scale, based on the summary of concentrations by dose, cohort and time post-dose).
- Individual concentration time plots by dose (on both linear and semi-log scales) against actual time post-dose (there will be separate spaghetti plots for each dose per scale) for each study treatment separately.

The length of time used for the x-axes of these plots will be decided on review of the data, and will depend on how long PF-07059013 concentration is quantifiable in the matrix.

For summary statistics, median and mean plots by sampling time, the nominal PK sampling time will be used, for individual subject plots by time, the actual PK sampling time will be used.

Urine PF-07059013 PK (Part 2 only) concentration and sample collection volumes will be listed by cohort, dose and subject. The urine PK parameters listed below in Table 6 will be summarized descriptively.

**CCI**

CCI	CCI
CCI	CCI

The comparison of formulation of PF-07059013 with and without PVP will be performed according to the Pfizer's Clinical Pharmacology Guidance Chapter 5 for analysis of absolute and relative bioavailability studies using repeated measures ANOVA on natural log-transformed blood **CCI** for the two dose levels separately. The results of analyses will be presented in tabular format including model estimates of geometric means for each group, adjusted geometric means ratios (Test/Reference) and 80% confidence interval for the ratios.

CCI

[figure not shown]

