4. STUDY DESIGN

4.1. Overall Design

This study consists of 3 parts, with ongoing review of safety, tolerability, PK and PD data planned.

Part 1 – Single Ascending Dose

The design for Period 1 to 3 for Part 1 of this study is investigator- and participant-blinded, sponsor-open, randomized, single ascending dose, with 3-period placebo substitution crossover, while Period 4 will be open-label. There will be 2 interleaving cohorts of healthy adult participants, with a total of approximately 18 participants planned (approximately 9 participants in each cohort). Each participant may receive up to 3 single oral doses of PF-07059013 and up to 1 placebo dose. For Period 1 to 3, at each period, approximately 6 participants will receive a single dose of PF-07059013 oral suspension formulated with polymer, and approximately 3 participants will receive placebo. In Period 4, a single dose of PF-07059013 oral suspension, formulated without polymer, will be administered at a dose level that has been previously administered in the same cohort.

Part 2 – Multiple Ascending Dose

Part 2 of this study will be investigator- and participant-blinded, sponsor-open, randomized, placebo-controlled, sequential, multiple ascending dose. A total of approximately 24 healthy adult participants will be randomized for Cohort 3 to 5. In each cohort, approximately 6 participants will receive PF-07059013 oral suspension (either with or without polymer, depending on results from Part 1) and approximately 2 participants will receive placebo, over a duration of 14 days, depending on randomization. Two additional cohorts (optional Cohort 6 and 7) with approximately 8 participants each, with the same randomization ratio may be included to permit assessment of any of the following: repeat of a previously administered dose level; studying additional dose levels as dictated by the evaluated safety, tolerability or PK of earlier dose levels; or any other assessment needed to meet the objectives of this study.

The first dose level in Part 2 will only initiate after review of safety and PK data from both cohorts in Part 1 Period 4. Refer to [Section 4.3.3](#) for additional details regarding determination of initial dose in Part 2 relative to dose(s) evaluated in Part 1.

Part 3 – Formulation and Food Effects

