600	110	0.6	0.0972	2100	12	1.94	15.4	11.6	7.4
1200	350	1.1	0.150	7100	25	3.10	10.0	7.26	22
2000	700	1.9	0.308	15000	41	6.64	4.87	3.39	45

- a. Depending on the available safety and PK data, dose escalation may be adjusted to doses other than those outlined above with intermediate doses evaluated instead of or in addition to the planned dose levels with increments being $\leq\frac{1}{2}\text{-log}$ (ie, 3.3-fold) while following dose escalation and stopping rules outlined in [Section 6.6.1](#).
- b. Human exposure was predicted based on a minimal PBPK model using in vitro data and SimCYP predictions.
- c. Derived using exposure of PF-07059013 at NOAEL (1000 mg/kg/day) from 1 month dog toxicity study of unbound $C_{max} = 1.5 \mu\text{g}/\text{mL}$ and $AUC_{24} = 22.5 \mu\text{g}\cdot\text{hr}/\text{mL}$.
- d. Unbound values calculated taking into account plasma protein binding in humans($f_{up}=0.162$).

4.3.3.3. Rationale for Dose Selection in Part 3

Depending on emerging data from Part 1 (and if available, data from Part 2), if Part 3 is conducted, a single dose level of PF-07059013 will be studied, and the dose selected will be lower than the highest dose found to be safe and well tolerated in Part 1. Furthermore, the dose selected will be in the range of likely pharmacologically active doses.

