9.4.2.2. Statistical Methods for PK Data

No formal inferential statistics will be applied to the PK data from Part 1 and 2.

Part 1 and Part 2

The PK parameters listed in **Table 3** and **Table 4** will be summarized descriptively by dose, treatment group (where applicable) and day (for Part 2). The blood and plasma concentration of PF-07059013 will be listed and descriptively summarized by nominal PK sampling time and treatment group. Individual participant, as well as mean and median profiles of the blood and plasma concentration-time data will be plotted by treatment group using actual (for individual) and nominal (for mean and median) times respectively. Mean and median profiles will be presented on both linear and log scales.

Dose normalized (to 1 mg) AUC and C_{max} of PF-07059013 will be plotted against dose (using a logarithmic scale) for single- and multiple dose phases, and will include individual participant values as well as the geometric means for each dose. These plots will be used to help understand the relationship between the PK parameters and dose.

Urine amounts of PF-07059013 **CCI** will be listed and summarized descriptively, if data permits.

Additional specifications about the tables, listings, and figures will be outlined in the SAP.

Food Effect and Formulation Evaluation

The pharmacokinetic parameters **CCI** C_{max} , and T_{max} for PF-07059013 will be summarized descriptively by treatment group. For **CCI** C_{max} , individual participant parameters will be plotted by treatment group. Blood and plasma concentrations will be summarized descriptively by treatment group, fed versus fasted condition, and PK sampling time. Individual participant, as well as mean and median profiles of concentration-time data will be plotted by treatment group using actual and nominal times, respectively. Mean and median profiles will be presented on both linear and log scales.

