The statistical comparison of PF-07059013 PK parameters following high-fat/high-caloric meal (Test) versus overnight fast (Reference), moderate particle size (Test) versus small particle size (Reference) suspension administered under fasted condition, and tablet formulation (Test) versus small particle size suspension formulation (Reference) administered under fasted condition will be detailed in the SAP. The analyses will include reporting the ratio of adjusted geometric means (Test/Reference) and 90% confidence intervals for the ratios for C_{max} , **CCI** as data permit.

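### Should the 80% interval for the with- versus without-polymer ratio be changed, given that the no-polymer suspension is given only in Period 4?

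*SAP*

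**What the plan says.** SAP 8.2.1 (Pharmacokinetic Analysis) states that "The comparison of formulation of PF-07059013 with and without PVP will be performed" following an internal sponsor guidance chapter, "using repeated measures ANOVA on natural log-transformed blood" exposure (the parameter name is redacted), "for the two dose levels separately". The output is geometric means per group and "adjusted geometric means ratios (Test/Reference) and 80% confidence interval for the ratios".

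The paragraph does not name the study part, but it must mean Part 1. Protocol 4.3.3.3 says of Part 3 that "a single dose level of PF-07059013 will be studied". Part 1 has two cohorts, each of which repeats an earlier dose without polymer, and it is the only planned within-participant comparison of the suspension with and without polymer.

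Protocol 9.4.2.2 states: "No formal inferential statistics will be applied to the PK data from Part 1 and 2". For the Part 3 food, particle-size and tablet comparisons it plans the "ratio of adjusted geometric means (Test/Reference) and 90% confidence intervals for the ratios".

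On the order of treatments, protocol 4.1 says: "In Period 4, a single dose of PF-07059013 oral suspension, formulated without polymer, will be administered at a dose level" already used in that cohort. Periods 1 to 3 use the suspension with polymer, with about 6 active and 3 placebo participants per period. Protocol 4.1 makes Period 4 open-label, and SAP 2.1 says it is not randomized.

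**The concern.** Three things look wrong together. The SAP runs a model with confidence intervals where the protocol says there will be no inference. It uses 80%, while the protocol uses 90% for the study's other formulation ratios, so the polymer result could look more precise than its neighbours. And every no-polymer dose falls in Period 4 while every with-polymer dose falls earlier, so the ratio mixes formulation with whatever changed between periods.

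Protocol 2.2.4 says the polymer data will help select the product's composition, and protocol 4.1 makes the Part 2 formulation depend on Part 1. If the ratio were read as a clean, period-adjusted formulation effect with a tight interval, the choice could rest on more certainty than the design supplies.

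**Working it through.** The documents give no power, alpha, equivalence margin or within-participant CV for this comparison, so there is no planned figure to reproduce. What can be checked is the amount of information, whether the formulation effect can be estimated, and the effect of the confidence level.

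**1. Information per dose level.** Nine participants at 2:1 give 9 × 2/3 = 6 with-polymer observations at the matched dose, and Period 4 gives 9 without polymer. About 6 participants have both. With participant as a fixed effect, the error df are 15 observations − 9 participants − 1 formulation effect = 5.

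**2. Estimability.** For one dose level, a model with participant and period has rank 9 + 1 = 10. Adding a formulation term leaves the rank at 10, because its column equals the Period 4 column. Pooling all periods of both cohorts with dose terms does not help: the rank stays at 23 or 24 (depending on which earlier dose is repeated) with and without formulation. Hence

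log(observed ratio) = log(formulation effect) + log(Period 4 effect) + error,

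and any period drift enters one for one. This holds for the ANOVA and equally for paired log differences.

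**3. Effect of the confidence level.** On 5 df, t = 1.476 for 80% and 2.015 for 90%. The width ratio on the log scale is 1.476/2.015 = 0.73, so the 80% interval is 27% narrower. With 6 pairs and an observed ratio of 1.00, the limits are exp(± t × √ln(1 + CV²) × √(2/6)). The CVs are assumptions:

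| CV | 80% CI | 90% CI |
|---|---|---|
| 15% | 0.88–1.14 | 0.84–1.19 |
| 20% | 0.84–1.18 | 0.79–1.26 |
| 30% | 0.78–1.28 | 0.71–1.41 |
| 40% | 0.72–1.39 | 0.64–1.57 |

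For CV 30%: √ln(1.09) = 0.294 and √(2/6) = 0.577, so the half-widths are 1.476 × 0.1695 = 0.250 and 2.015 × 0.1695 = 0.342. The upper limits are then 1.28 and 1.41.

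**4. Carryover as a source of period drift.** Protocol 4.3.1 projects a longest effective half-life of 41 hours (at 3000 mg). The minimum washout of 14 days is 336/41 = 8.2 half-lives, which leaves 2^(−8.2), about 0.3%.

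**5. Authority for the departure.** The opening of protocol Section 9 allows the SAP to modify the protocol's outline where appropriate, and requires an amendment only for major changes to primary endpoints or their analyses. Protocol Section 3 makes the primary endpoints safety measures; PK exposure is secondary. SAP 8.2.1 itself calls the main analyses of all three parts descriptive, and the PVP paragraph gives estimates and intervals with no test.

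**The case for a change.** The best case for a change is that it would be cheap and that the aliasing is certain. A model-based ratio with an interval is inferential in the ordinary sense, the two documents disagree, and the visible SAP text neither flags the departure nor explains the 80%. Calling the ratio adjusted, with no caveat, may lead a reader to assume that period has been handled. SAP 2.1 also sets a Part 3 tablet without PVP against a suspension with PVP, so the Part 1 polymer ratio is a natural companion to the tablet ratio, and a common confidence level would make the two easier to read together.

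The aliasing, the count of about 6 pairs and the unflagged mismatch in wording all stand. The rest weakens on inspection:

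- The SAP does not claim to adjust for period. Adjusted means can simply be model means that account for participant when 6 observations are set against 9.
- The confidence level that the SAP uses for Part 3 lies in redacted text, if it is given, so it is not established that the final tables would mix 80% and 90%. A rationale for 80% could likewise lie in redacted text, including SAP Section 4.
- The fixed order is deliberate. Protocol 4.2 explains that escalation uses the polymer suspension because it may raise exposure, so that safety is seen at the potentially higher exposures before the no-polymer product is given.
- A 90% level and paired differences would not cure the problem that gives the concern its force. Both carry the same Period 4 effect and rest on the same 6 or so pairs.

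**Conclusion.** The concern is right about the facts, but it leads to no change. Formulation and period are inseparable in Part 1 under any analysis. That is the price of a safety-driven order, it is disclosed in protocol 4.2 and SAP 2.1, and only a different design could remove it. The choice of 80% or 90% is a matter of convention for an exploratory ratio with no visible margin or decision threshold. It changes the width by a known 27% on the log scale, and the level is stated with the result, so a reader can convert one to the other. The mismatch with protocol 9.4.2.2 is within what Section 9 of the protocol permits for a non-primary endpoint. A competent report author will describe the ratio as a fixed-sequence, exploratory estimate that assumes no period effect, without needing an amendment to do so.

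This rests on four assumptions: that the PVP paragraph refers to Part 1; that about 6 participants per dose level receive both formulations; that within-participant CV lies somewhere around 15% to 40%; and that no redacted text ties the formulation choice to a limit of this interval. The CV affects only the illustrated widths, not the 27% or the aliasing.
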